Maternal Choline Supplementation and Offspring Cognition in Adolescence

NCT05859126

28 June 2024

This study seeks to test the general hypothesis that maternal choline intake of 930 mg/d throughout the 3rd trimester of pregnancy, compared to 480 mg/d, causes offspring to have superior cognitive functioning. Three domains of cognition will be examined to test three independent hypotheses about the effects of the intervention on (1) sustained attention, (2) executive functioning, and (3) memory.

Sample Size:

The sample size was determined by the original controlled feeding study, which was designed to detect group differences for that study's primary endpoints—biomarkers of choline status—for which it was estimated that a sample size of 26 (13 per treatment group) would achieve 80% power to detect a moderate effect size at an  $\alpha$  of 0.05. The sample sizes for the ancillary longitudinal follow-up studies to investigate treatment effects on infant and child cognitive outcomes was limited by the original sample size, minus loss to follow-up. The results of these studies demonstrated that (1) a sample size of 24 (12 per group) was sufficient to detect a statistically significant treatment effect of the prenatal choline intervention on infant processing speed (Caudill, et al., 2018) and (2) that a sample size of 20 (11/9 participants from the 930/480 mg choline/d groups, respectively) was sufficient to demonstrate group differences on several cognitive outcomes age 7 years. No further sample size calculations were conducted for this 14-year follow-up study because the sample was limited to those included in the original feeding study, which was sufficient to see the effect of choline on cognition. We hypothesize that the cognitive effects of the prenatal supplementation should endure into adolescence, and we expect that the cognitive outcomes will be measured with much greater precision at age 14 years than during infancy or at 7 years, thus we expect to have adequate power to detect similarly moderate to large effect sizes.

Descriptive Statistics:

Univariate and bivariate descriptive statistics and graphs will be examined to assess data value plausibility. Descriptive statistics for sample characteristics, by group, will be presented in tables. Continuous variables will be summarized with means and standard deviations, and categorical variables will be summarized with absolute counts and relative frequencies. A table of sample characteristics will include participant sex, level of education, parental level of education, native language, family income, history of head injury absence/presence, and concurrent medications and supplements. We will also provide a flow chart detailing participant attrition and missing data.

Inferential Statistical Analysis:

Acknowledging the risks inherent with utilizing multiple endpoints in a small sample, we generated an *a priori* analysis plan, with specific objectives in alignment with the areas of cognition of interest. For each cognitive objective, we have detailed the tasks and outcome variables that will be used for its measurement.

Objective 1 Sustained Attention: Estimating the effect of maternal third trimester choline intake on offspring **sustained attention** at age 14 years.

- **Sustained Attention** will be measured using the Rapid Visual Information Processing task (RVP) of the Cambridge Neuropsychological Test Automated Battery (CANTAB).
  - **The primary outcome for this objective will be the nonparametric index of detection sensitivity, A-prime.**
    - A-prime will be analyzed using a general linear model with fixed effects of treatment group and participant sex.

Objective 2 Executive Functioning: Estimating the effect of maternal third trimester choline intake on offspring **executive functioning** at age 14 years.

- Our primary outcome for this objective will be a composite measure of executive functioning (EF) derived from key variables obtained from multiple tasks that assess four core components of EF: planning, working memory, inhibitory control, and attentional flexibility. All tasks are administered using the CANTAB platform.
  - **Planning** will be assessed by two versions of a Towers of London task. The key outcome variable from the **Stockings of Cambridge task (SOC)** will be the **number of perfect solutions across all problems**. From the **One Touch Stockings of Cambridge task (OTS)** the **key outcome** variable will be the number of problems solved on the first attempt.
  - **Working Memory** will be assessed using the **Spatial Working Memory task (SWM)** and the Backward Digit Span task (BDS). The key outcome variable for SWM will be the total number of search errors and span length for BDS.
  - **Inhibitory control** will be assessed using the **Cambridge Gambling Task (CGT)**. The key outcome variable will be the delay aversion total score.
  - **Attentional flexibility** will be assessed using the **Intradimensional-Extradimensional Shift task (IED)**. The key outcome variables will be the total number of choice errors.
- The EF composite (EFcomp) outcome variable will be defined as the average z-score of the individual key EF task outcomes as follows: EFcomp = (zSOC perfect solutions+ zOTS first attempt correct+ zSWM search errors+ zBDS span length+ zCGT delay aversion+ zIED choice errors) / 6

with the z-score calculated by the sample mean and standard deviation:

$$z = \frac{\text{raw score} - \bar{x}_{\square}}{sd_{\square}}$$

Statistical analysis of EFcomp will be conducted using a general linear model with fixed effects of treatment group and participant sex.

Objective 3 Memory: Estimate the effect of maternal third trimester choline intake on offspring **memory function** at age 14 years.

- Our primary outcome for this objective will be a composite measure of memory function derived from multiple tasks assessing episodic memory, recognition memory, and working memory. All tasks are administered using the CANTAB platform.
- **Episodic memory** will be assessed by a Verbal Paired Associate Learning task (VPA) and a nonverbal **Paired Associate Learning task (PAL)**. The key outcome for both tasks will be the total number of errors.
- **Recognition memory** will be assessed by the **Delayed Match to Sample task (DMS)** and the **Pattern Recognition Memory task (PRM)**. The key outcome for both tasks will be the proportion of correct choices on delay trials.
- **Working memory** will be assessed using two span tasks: **nonverbal spatial span (SSP)** and verbal forward digit span (FDS). The key outcome variable for both will be span length.
- The memory composite ( $MEM_{comp}$ ) outcome variable will be defined as the average z-score of the individual key outcomes from the memory tasks as follows:  $MEM_{comp} = (zVPA \text{ total errors} + zPAL \text{ total errors} + zDMS \text{ proportion correct} + zPRM \text{ proportion correct} + zSSP \text{ span length} + zFDS \text{ span length}) / 6$

with the z-score calculated by the sample mean and standard deviation:

$$z = \frac{\text{raw score} - \bar{x}_{\square}}{sd_{\square}}$$

Statistical analysis of  $MEM_{comp}$  will be conducted using a general linear model with fixed effects of treatment group and participant sex.

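### Does the SAP need a rule for how its three domain tests bear on the general hypothesis of superior cognition?

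*SAP*

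**What the plan says.** The SAP's opening paragraph begins "This study seeks to test the general hypothesis that maternal choline intake of 930 mg/d throughout" the third trimester, compared with 480 mg/d, "causes offspring to have superior cognitive functioning". The sentence after it reads "Three domains of cognition will be examined to test three independent hypotheses about the effects of the intervention", and the paragraph lists sustained attention, executive functioning and memory.

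The section on Inferential Statistical Analysis names the multiplicity risk and answers it by fixing objectives and outcomes beforehand: "Acknowledging the risks inherent with utilizing multiple endpoints in a small sample, we generated an" analysis plan in advance. Each objective then has one primary outcome. For Objective 1, "The primary outcome for this objective will be the nonparametric index of detection sensitivity, A-prime". Objectives 2 and 3 use the composites EFcomp and MEMcomp. All three are analysed in separate linear models with terms for group and sex.

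The Sample Size section looks back at the earlier follow-ups. It says that 20 children (11 and 9 by group) "was sufficient to demonstrate group differences on several cognitive outcomes age 7 years", and it describes the feeding-study sample as one "which was sufficient to see the effect of choline on cognition".

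**The concern.** A hypothesis that is announced as tested should have a test, or a rule that derives its verdict from other tests. Here the general hypothesis has neither. The SAP does not say whether one, two or all three domains must be positive before general superiority may be claimed.

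The Sample Size section makes the worry less abstract. It passes from an effect on infant processing speed and differences on some age-7 outcomes to a statement about choline and cognition as a whole. If the age-14 report took the same step from a single positive domain, the general causal claim would rest on the best of three tests and would carry more than one test's false-positive risk.

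**Working it through.** **1. What is tested.** The specified primary analyses are three: A-prime, EFcomp and MEMcomp, one model each. The psychological-health comparisons are exploratory, and the secondary and post-hoc analyses are left open. None of these is described as a test of the general hypothesis, and no any-one, two-of-three or all-three rule appears anywhere.

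**2. Inputs.** The SAP states no error rate for the three tests. Its only alpha, 0.05, belongs to the feeding study's biomarker calculation (26 women, 80% power, a moderate effect). That figure cannot be reproduced because the moderate effect has no number, and nothing below depends on it. The level and sidedness of the age-14 tests are therefore assumptions, and both common choices are shown.

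**3. False superiority if any one positive domain counted as general support.** Let a be the error of each test in the favourable direction.

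- Independent tests: 1 − (1 − a)³. Upper bound under any dependence: 3a.
- Two-sided 0.05, so a = 0.025: 1 − 0.975³ = 0.0731; bound 3 × 0.025 = 0.075.
- One-sided 0.05, so a = 0.05: 1 − 0.95³ = 0.1426; bound 3 × 0.05 = 0.15.

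The SAP calls the hypotheses independent. The test statistics come from the same adolescents and are probably correlated. Simulation with a common correlation r gives:

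| r | a = 0.025 | a = 0.05 |
|---|---|---|
| 0.3 | 6.8% | 12.9% |
| 0.5 | 6.3% | 11.9% |
| 0.7 | 5.5% | 10.2% |
| 0.9 | 4.2% | 7.9% |

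**4. False superiority under the other readings.** If domains are concluded on separately, each claim keeps its own a (2.5% or 5%). If all three were required for the general claim, the error could not exceed a. The inflation therefore belongs to the any-one reading alone.

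**5. Would adding a global test help?** The obvious candidate is the mean of the three standardised primary outcomes, in the same model. Take the age-7 numbers (11/9), an assumed r = 0.5 and two-sided 0.05. The SD of the mean is √[(1 + 2 × 0.5)/3] = 0.816, and the group factor is √(11 × 9/20) = 2.225. With an assumed 0.8 SD effect in every domain, the noncentrality is 0.8/0.816 × 2.225 = 2.18. If only one domain responds it falls to a third of that, 0.73. Simulated power:

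| Assumed effect | Mean of three | Holm across domains |
|---|---|---|
| 0.8 SD in all three | 53% | 43% |
| 0.5 SD in all three | 25% | 20% |
| 0.8 SD in two | 26% | 35% |
| 0.8 SD in one | 9% | 23% |

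Read as a fourth test beside the domain tests, it would also raise the chance of at least one false superiority claim, under independence, from about 7.2% to 8.2% in simulation.

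**The case for a change.** The strongest case for a change is that this is a fault in what the document states, not detail left to a protocol: it names a hypothesis as tested and gives no test of it. Fixing outcomes in advance protects the domain tests but not the step from them to a general causal claim. The Sample Size section has already made a step of that kind, and further analyses are left open. One or two sentences would settle the matter at no cost in data or power.

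The textual observation stands: no sentence links the domain results to the general statement. The rest does not carry the weight.

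- The sentence straight after the general hypothesis translates it into three hypotheses, and the objectives follow that structure exactly. An analyst would report three domain results.
- The Sample Size remark explains why no new calculation was made. It concerns earlier data and sets no rule for this follow-up. That the step might be repeated is conjecture.
- Low cost is not a reason to require a change that alters no model, no estimate and no p-value.
- A global test is a trade-off: better if all three domains respond, worse if only one or two do. Nothing in the SAP says which pattern to expect.

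Any directional global rule would also need all components of EFcomp and MEMcomp scored so that higher means better. That scoring is a separate matter and neither strengthens nor weakens this point.

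**Conclusion.** No change follows. The general hypothesis is framing, the testable content is the three domain hypotheses, and one primary outcome with one model for each is a sound structure for separate conclusions. The excess error (7.3%, at most 7.5%, with an assumed two-sided 0.05; 14.3%, at most 15.0%, with one-sided 0.05) depends on a future any-one-domain reading that the SAP does not adopt. Read by domain, nothing is inflated. The authors could tidy the opening sentence, but that would only record the interpretation the plan already invites. The power figures rest on assumed effects of 0.5 or 0.8 SD, a correlation of 0.5 and the age-7 group sizes. They show that a global test is a choice, not a correction.

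### The SAP expects adequate power for moderate to large effects at age 14 without a calculation; at an assumed d = 0.5 the planned model gives 18–23% two-sided, and only stacked, unstated assumptions bring it near 80%

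*SAP*

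**What the plan says.** The Sample Size section first gives the original feeding study's basis: 26 women, 13 per group, 80% power for a moderate effect at alpha 0.05, on biomarkers of choline status. For age 14 it states: "No further sample size calculations were conducted for this 14-year follow-up study". The expectation of power then rests on two arguments.

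- **Earlier results.** In infancy "a sample size of 24 (12 per group) was sufficient to detect a statistically significant treatment effect" on processing speed. At 7 years a sample of 20 (11 and 9) "was sufficient to demonstrate group differences on several cognitive outcomes age 7 years". The SAP sums this up by saying that "the sample was limited to those included in the original feeding study, which was sufficient to see the effect of choline on cognition".
- **Precision.** The authors write that "we expect that the cognitive outcomes will be measured with much greater precision at age 14 years than during infancy or at 7 years".

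From these it concludes: "thus we expect to have adequate power to detect similarly moderate to large effect sizes".

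Under Inferential Statistical Analysis, Objective 1 fixes the model: "A-prime will be analyzed using a general linear model with fixed effects of treatment group and participant sex". Objectives 2 and 3 use the same model, each on the mean of six task z-scores. That section opens with a caution, "Acknowledging the risks inherent with utilizing multiple endpoints in a small sample", and the closing section on secondary and exploratory analyses again mentions the small sample. Neither place qualifies the power sentence.

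**The concern.** This is the SAP's only statement about power at age 14, and it covers all three primary outcomes. It is a forward claim without a number behind it: moderate and large are not defined, and sidedness, the N expected at age 14 and the size of the precision gain are not given.

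What is at stake is how a null result is read. A reader who accepts that power was adequate for a moderate effect may take a non-significant difference as evidence against one. With 20 to 26 adolescents, the data could not support that at d = 0.5.

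**Working it through.** **Inputs.** Group sizes 13/13, 12/12 and 11/9 are the original, infant and 7-year samples in the Sample Size section; N at age 14 is not stated. The model is treatment plus sex, so residual df = N − 3. Assumptions of mine: alpha 0.05; d = 0.5 (moderate) and 0.8 (large), in residual SD units; sex balanced across groups, which is the favourable case. Both sidednesses are shown, because the general hypothesis is directional but no test direction is fixed.

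**The SAP's own figure.** The 80% belongs to the original study. An ordinary two-group t test with 13 per group and d = 0.5 has 23% power two-sided and 34% one-sided, so the figure does not reproduce that way. A one-sided one-sample or paired test with N = 26 gives 79.8%, and some repeated-measures tests give 80% or more. That study's design is not shown, so its figure can be neither confirmed nor faulted. There is no figure for age 14 to reproduce.

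**Formula.** Power is the noncentral-t tail probability with df = N − 3 and noncentrality d / √(1/n₁ + 1/n₂). The root is 0.392, 0.408 and 0.450 for the three sample sizes, so at d = 0.5 the noncentrality is 1.27, 1.22 and 1.11.

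**Scenarios.**
- A precision gain of 1.41 (residual variance halved) is assumed: 0.5 × 1.41 = 0.705 and 0.8 × 1.41 = 1.128.
- For a composite of six tasks with equal d, all scored in one direction, and mean correlation r, d_comp = d × √(6 / (1 + 5r)). At r = 0.3 the factor is √(6/2.5) = 1.55. With d = 0.5 this gives 0.775 without the gain and 0.5 × 1.41 × 1.549 = 1.09 with it.

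| Power (%), two-sided / one-sided | 13/13 | 12/12 | 11/9 |
|---|---|---|---|
| d = 0.5 | 23.1 / 34.2 | 21.5 / 32.3 | 18.3 / 28.2 |
| d = 0.5, gain 1.41 (single score) | 40.6 / 54.0 | 37.8 / 51.0 | 31.6 / 44.5 |
| Composite, d = 0.5 per task, r = 0.3, no gain | 47.3 / 60.7 | 44.1 / 57.6 | 36.9 / 50.4 |
| Composite, d = 0.5 per task, r = 0.3, gain 1.41 | 76.0 / 85.5 | 72.3 / 82.7 | 63.0 / 75.4 |
| d = 0.8 | 49.8 / 63.1 | 46.4 / 59.9 | 39.0 / 52.5 |
| d = 0.8, gain 1.41 | 78.6 / 87.4 | 75.0 / 84.8 | 65.8 / 77.7 |
| Detectable d at 80% power | 1.15 / 1.01 | 1.20 / 1.05 | 1.34 / 1.17 |

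**Sensitivity of the composite row.** Better reliability may also raise the between-task correlation. At r = 0.4 with the gain, power is 55–68% two-sided and 69–79% one-sided. In the other direction, 80% two-sided at 13/13 needs a composite factor of 1.148 / 0.705 = 1.628, that is r ≤ (6/1.628² − 1)/5 ≈ 0.25. At 11/9 it needs 1.336 / 0.705 = 1.895, that is r ≤ (6/1.895² − 1)/5 ≈ 0.13.

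**Gain needed for a single score at d = 0.5.** Two-sided: 1.148 / 0.5 = 2.30 at 13/13, up to 1.336 / 0.5 = 2.67 at 11/9. One-sided: 2.01 to 2.33.

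**Earlier significance.** A single two-sided two-group t test reaches p < 0.05 only if the observed d is at least about 0.85 (12/12) or 0.94 (11/9). With a true d of 0.5 and 12 per group, the planned model would still be significant about one time in five. A significant result therefore does not show that power was adequate, and the earlier outcomes were not the three now planned.

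**What a null estimate would exclude.** The expected 95% CI half-width is t(0.975, N − 3) × √(1/n₁ + 1/n₂): 2.069 × 0.392 = 0.81 SD at 13/13, 0.85 SD at 12/12, and 2.110 × 0.450 = 0.95 SD at 11/9. An estimate of zero remains compatible with 0.5 SD at every N, and with 0.8 SD only just at 13/13.

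**The case against.** The strongest reply is that d = 0.5 is an outside convention. The word similarly may point back to the effects seen earlier, whose sizes are not given. If those were about 0.85 at 12/12 and 0.94 at 11/9 (just significant in a simple two-group test), the same 1.41 gain would give about 80% and 79% two-sided. That stands as a warning that the answer turns on the referent. It does not show adequacy: effects picked out because they were significant tend to be too large, and the SAP still names moderate as its lower end. Reading moderate more generously as f² = 0.15 (d about 0.77) gives 37–47% two-sided and 51–61% one-sided without a gain.

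A second reply is that precision and averaging act together on two of the three primary outcomes. This is right, and it narrows the point. A reader might infer from the single-score rows that one-sided power for a moderate effect cannot exceed 54%. That holds for A-prime under the assumed gain, not for the composites, where the combined scenario passes 80% one-sided at 13/13 and 12/12. It does so only with tasks scored in one direction, and the printed formulas add error scores to accuracy and span scores with no sign reversal shown.

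Third, N is fixed by the original cohort and the SAP acknowledges the small sample. Both are true, and nobody could ask for more participants. But a fixed N does not make power adequate, and the acknowledgements leave the sentence unqualified.

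**Conclusion.** The point holds in a limited form. The power expectation for age 14 is unsupported, and at a conventional moderate effect it is not met by the planned model as it stands: 18–23% two-sided, 28–34% one-sided. In the scenarios tabulated, two-sided power for a moderate effect stays below 80%. One-sided power reaches 80% only for the composites, and only when the gain, a modest between-task correlation, consistent scoring direction and at least 24 participants are all assumed. The SAP states none of these. The conclusion rests on d = 0.5, alpha 0.05 and N between 20 and 26.

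Three stronger readings are not supported:
- **That power fails for large effects too.** At d = 0.8 it is 39–50% two-sided without a gain and 66–79% with it (78–87% one-sided). A composite with 0.8 per task and r = 0.3 corresponds to 0.8 × 1.549 = 1.24, above the two-sided detectable difference at 13/13 and 12/12. This end depends on what is assumed.
- **That the original study's 80% is wrong.** It concerned biomarkers, under a design not shown.
- **That the SAP treats a non-significant result as ruling out an effect.** It nowhere says so; the risk lies in how the sentence may be used.

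**What to change.** In the Sample Size section:

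1. Remove the inference from earlier significant results to power at age 14.
2. Replace the power sentence with the N expected at 14 years, the sidedness, and the minimum detectable standardised difference at 80% power. At alpha 0.05 this is about 1.15 SD (13/13) to 1.34 SD (11/9) two-sided, or about 1.01 to 1.17 SD one-sided.
3. Say what standardised differences are meant by moderate and large.
4. State that power for a difference of 0.5 SD on the analysed outcome is low, so a non-significant result cannot exclude it and must be read from the estimate and its 95% CI (about ±0.81 to ±0.95 SD).
5. If the precision or composite argument is kept, give the assumed gain and between-task correlation and their basis.

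The cost is wording only, and the stated power becomes less favourable. Participants, endpoints, model and test do not change.

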#### Secondary, post-hoc, and exploratory analyses

Given our small sample size, the complexity of the interpretation of cognitive tests, and the novelty of this research. We will, as appropriate conduct additional planned secondary and

sensitivity analyses, in addition to post-hoc exploratory analyses to better understand our data to arrive at the fullest possible understanding of the effects of the intervention.

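### Should the three primary models adjust for parental education as well as sex?

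*SAP*

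**What the plan says.** Under Inferential Statistical Analysis, the SAP gives one model for all three objectives. For sustained attention, "A-prime will be analyzed using a general linear model with fixed effects of treatment group and participant sex". For the executive-function and memory composites, the analysis "will be conducted using a general linear model with fixed effects of treatment group and participant sex".

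Parental education appears once, under Descriptive Statistics: "A table of sample characteristics will include participant sex, level of education, parental level of education, native language, family income". The SAP does not say which parent is meant, how the variable is coded, when it is measured or how complete it is.

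On numbers, the Sample Size section says that the size of the earlier follow-ups "was limited by the original sample size, minus loss to follow-up". The last one it reports, at age 7, had "a sample size of 20 (11/9 participants from the 930/480 mg choline/d groups, respectively". No size is given for age 14.

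The last section, on secondary, post-hoc and exploratory analyses, provides for planned secondary and sensitivity analyses "in addition to post-hoc exploratory analyses to better understand our data". It names no covariate.

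**The concern.** Family background plausibly relates to cognitive test scores, and in a sample this small the two groups can easily differ on it by chance. A model that leaves it out is right on average over repeated allocations. There is only one cohort, however, and it cannot be enlarged, so a realised imbalance would push the one estimate obtained in a known direction. The plan would display that imbalance in its by-group table without having said beforehand what to do about it, and any adjustment added later could look chosen to suit the result. Loss to follow-up seems to add to the worry, because the groups went from 12/12 in infancy to 11/9 at age 7. Against this, one extra model term looks cheap. What would be at stake is precision and the credibility of the primary contrasts.

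**Working it through.** **Inputs.** From the SAP: treatment plus sex in each model; 11/9 at age 7; 13 per group originally. Assumed, because the SAP does not give them: 11/9 again at age 14, random allocation, a true effect of d = 0.8 SD, and a correlation r between parental education and the outcome, varied from 0 to 0.5.

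**The plan's own power figure.** The SAP states that "it was estimated that a sample size of 26 (13 per treatment group) would achieve 80% power to detect a moderate effect size"; the significance level there was 0.05. Moderate carries no number, so this cannot be reproduced strictly. At d = 0.5, 13 per group gives 23% (two-sided t test); 80% is reached at d of about 1.15. The figure concerns biomarkers in the feeding study and has no bearing on which covariates belong in the present models.

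**Step 1: average cost and gain of one linear term.** Relative to the sex-only model, the expected variance of the treatment contrast is multiplied by (1 − r²)(n − 4)/(n − 5).

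- n = 20: (n − 4)/(n − 5) = 16/15 = 1.067. Break-even is r² = 1 − 15/16 = 0.0625, so r = 0.25.
- n = 26: 22/21 = 1.048. Break-even is r² = 1 − 21/22 = 0.045, so r = 0.21.
- At r = 0 and n = 20, residual degrees of freedom fall from 17 to 16 and the critical t rises from 2.110 to 2.120. The interval widens by √1.067 × 2.120/2.110 = 1.04, about 4%.

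**Step 2: simulated power at 11/9, d = 0.8.**

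| r | SD of contrast, sex only | with covariate | Power, sex only | with covariate |
|---|---|---|---|---|
| 0 | 0.466 | 0.482 | 37% | 35% |
| 0.2 | 0.463 | 0.468 | 37% | 36% |
| 0.25 | 0.464 | 0.464 | 37% | 37% |
| 0.3 | – | – | 37% | 38% |
| 0.4 | 0.464 | 0.438 | 37% | 41% |
| 0.5 | 0.463 | 0.415 | 37% | 44% |

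Type I error lies between 0.047 and 0.053 in both models.

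**Step 3: is the shift from imbalance extra error?** The standardised imbalance has SD √(1/11 + 1/9) = 0.449. A one-SD imbalance moves the contrast by r × 0.449: 0.13 at r = 0.3 and 0.22 at r = 0.5. This is one component of the standard error of about 0.46 and is not added to it. It makes up a share r² of the sampling variance: 9% at r = 0.3, 25% at r = 0.5. The sex-only interval already allows for it.

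**Step 4: coding and missing values.** Entered as a four-level factor at 11/9, the covariate changes the 95% half-width from 0.97 to 1.08 at R² = 0, from 0.96 to 1.02 at R² = 0.10, and leaves it at 0.96 at R² = 0.20. Nothing is gained up to that point.

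The Missing Data section ties imputation to sensitivity analyses and compares results with and without it. In the analysis without imputation, a missing covariate value removes a participant. If one is lost (11/8), the adjusted variance is (1 − r²)(1/11 + 1/8)(16/14) = 0.247(1 − r²), against (1/11 + 1/9)(17/16) = 0.215 for sex only at 11/9. Break-even rises to r² = 1 − 0.215/0.247 = 0.13, so r = 0.36. At r = 0.3, simulated power is 35.5% for the adjusted model at 11/8 against 37.2% for sex only at 11/9.

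**Step 5: attrition.** If the infancy and age-7 cohorts are the same, the net losses are 1 of 12 and 3 of 12; Fisher's exact test gives p = 0.59. Nothing in the SAP links loss to parental education.

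**The case for a change.** The best argument for the covariate is conditional. At 11/9, about 26% of trials would show an imbalance above 0.5 SD. In those trials the sex-only estimate is off in the direction of the imbalance by 0.23 SD at R² = 0.10 and 0.39 SD at R² = 0.30, and coverage of the 95% interval falls to 94% and 90%. Adjustment restores both. Naming the term beforehand would also remove any suspicion of a post-hoc choice.

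The statistics of this are correct, and a statistician who believed the correlation to be 0.4 or more would have good reason to include the term. Three things keep it from being a fault in the plan.

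- The size of the conditional error depends wholly on a correlation that the SAP does not give. At R² = 0.10 the loss of coverage is about one point, and only in a quarter of trials. Overall coverage stays at 95%, so the remaining trials lie slightly above it: (0.95 − 0.263 × 0.937)/0.737 = 0.955.
- Parental education is one of several background variables in the table. Family income and native language have a similar claim, and the SAP gives no basis for ranking them. With about 20 participants, keeping the model small is defensible.
- The three primary models are already fixed. The closing section foresees planned as well as post-hoc analyses, and nothing found there replaces a primary result. An adjustment made after the table is seen would be exploratory.

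**Conclusion.** The concern does not hold. The SAP states the same treatment-plus-sex model for all three primary outcomes, does not contradict itself on it, and the model keeps its type I error at about 5%. Adding parental education would change power at 11/9 and d = 0.8 by about −2 points at r = 0, under +1 at r = 0.3 and about +8 at r = 0.5, with break-even near r = 0.25. A multi-level coding or a single missing value would raise the correlation needed. These figures rest on the age-7 split holding at age 14, on the assumed effect size and on random allocation, which the SAP does not itself describe. Within those limits, adjusting for sex alone is a legitimate prespecified choice, and adding parental education is an option the sponsor may weigh.

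### Both composite primary outcomes add error scores to accuracy and span scores with the same sign, so an equal benefit on every task cancels in EFcomp and leaves one third of the mean difference in MEMcomp

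*SAP*

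**What the plan says.** The opening paragraph of the SAP gives the hypothesis a direction: the higher choline intake "causes offspring to have superior cognitive functioning". Objectives 2 and 3 each take a composite as primary outcome, analysed by a general linear model on treatment group and sex.

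Objective 2 names six components:
- Stockings of Cambridge (SOC): "number of perfect solutions across all problems".
- One Touch Stockings (OTS): the "variable will be the number of problems solved on the first attempt".
- Spatial Working Memory (SWM) and Backward Digit Span (BDS): "The key outcome variable for SWM will be the total number of search errors and span length for BDS".
- Cambridge Gambling Task (CGT): the delay aversion score.
- Intradimensional-Extradimensional Shift (IED): the count of choice errors.

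The composite is then "zSOC perfect solutions+ zOTS first attempt correct+ zSWM search errors+ zBDS span length+ zCGT delay aversion+ zIED choice errors) / 6".

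Objective 3 is built the same way. For the verbal and nonverbal paired-associate tasks (VPA and PAL), "The key outcome for both tasks will be the total number of errors". DMS and PRM contribute proportions correct, and SSP and FDS contribute span lengths. All six z-scores are added and divided by 6.

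Under both objectives z is the raw score minus the sample mean, over the sample SD. No section reverses a score or says which direction of either composite is favourable.

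**The concern.** An average of z-scores measures one construct only if all its terms point the same way. Here a child who does better on every task gains on some terms and loses on others. Run as written, the composites do not measure executive function or memory on a scale from worse to better, and the group coefficient cannot be read as benefit or harm. A real effect could be missed, or could appear with the wrong sign, in two of the three primary outcomes. If the signs are instead settled during analysis, two primary outcomes rest on a decision that the plan does not record. The SAP presents itself as an a priori plan meant to limit the risk of multiple endpoints in a small sample, and that would undercut it.

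**Working it through.** The SAP gives no effect size or power for the composites, so there is no figure of its own to reproduce. The total of 26 under Sample Size belongs to the biomarker endpoints of the original feeding study and is not used here.

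**Step 1. Direction of each component** (s = +1 if higher is better, −1 if higher is worse)

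| Composite | Higher is better (+1) | Higher is worse (−1) |
|---|---|---|
| EFcomp | SOC perfect solutions, OTS first-attempt solutions, BDS span | SWM errors, IED errors, CGT delay aversion* |
| MEMcomp | DMS and PRM proportion correct, SSP and FDS span | VPA errors, PAL errors |

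*Inferred from the name and its use for inhibitory control. The SAP does not state the direction.

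**Step 2. Expected group difference for an equal benefit of d SD on every task:** d × Σs / 6

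- EFcomp as written: d(1 + 1 − 1 + 1 − 1 − 1)/6 = 0
- MEMcomp as written: d(−1 − 1 + 1 + 1 + 1 + 1)/6 = d/3
- Either composite, correctly oriented: 6d/6 = d

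**Step 3. Other readings of delay aversion**

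- Higher is better: d(1 + 1 − 1 + 1 + 1 − 1)/6 = d/3, against d when oriented. One third is kept.
- No effect on this score: d(1 + 1 − 1 + 1 + 0 − 1)/6 = d/6, against 5d/6 when oriented. One fifth is kept.

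**Step 4. Unequal benefits**

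- Benefit only on the three adverse EF scores: −3d/6 = −d/2, an apparent harm.
- Benefit only on the two paired-associate tasks: −2d/6 = −d/3, also an apparent harm.
- Task effects varying independently with assumed mean 0.5 and SD 0.2, floored at 0: the share of the oriented effect that is kept runs from about −0.33 to +0.33 in EFcomp and from about 0.02 to 0.65 in MEMcomp. A rough check for EFcomp is 2 × √6 × 0.2 / (6 × 0.5) = 0.33.

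**Step 5. Power, as an illustration.** Assumptions: n = 11 and 9 (the age-7 follow-up, under Sample Size; the age-14 numbers are not given), d = 0.5 or 0.8, and a common between-task correlation ρ after alignment.

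Composite variance = [6(1 − ρ) + ρ(Σs)²]/36. At ρ = 0.3:
- Oriented: (4.2 + 10.8)/36 = 0.417, SD 0.645
- EFcomp as written: 4.2/36 = 0.117, SD 0.342
- MEMcomp as written: (4.2 + 1.2)/36 = 0.150, SD 0.387

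At d = 0.8 the standardised effects are 0.8/0.645 = 1.24 oriented, 0 for EFcomp and 0.267/0.387 = 0.69 for MEMcomp. MEMcomp therefore keeps 0.69/1.24 = 0.56 of the standardised effect.

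Power comes from the noncentral t with noncentrality = standardised effect × √(11 × 9/20), 17 df (one spent on sex) and two-sided α = 0.05:

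| ρ | d | Oriented | EFcomp as written | MEMcomp as written |
|---|---|---|---|---|
| 0.1 | 0.5 | 55.5% | 5% | 14.1% |
| 0.1 | 0.8 | 91.8% | 5% | 28.7% |
| 0.3 | 0.5 | 36.9% | 5% | 14.8% |
| 0.3 | 0.8 | 73.9% | 5% | 30.4% |
| 0.6 | 0.5 | 25.1% | 5% | 16.0% |
| 0.6 | 0.8 | 53.8% | 5% | 33.5% |

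Simulation of the model on group and sex, at ρ = 0.3, agrees: about 35%, 4% and 14% at d = 0.5, and 70 to 72%, 3% and 29% at d = 0.8. With z-scores taken from the pooled sample, the simulated mean differences at d = 0.8 were 0.73 oriented, 0.00 in EFcomp and 0.245 in MEMcomp, a ratio of 0.245/0.73 = 0.34 against the exact one third.

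**The case against.** The strongest reply is that reverse-scoring errors is routine and the analysts surely intend it. That may be so, but the SAP writes out the full formula and the full z-score definition, and neither contains a reversal. A lost minus sign is unlikely, since both composites show plus signs throughout while the minus in the z-score formula is intact. The graphical checks under Descriptive Statistics and the additional analyses in the last section might expose the problem, but neither commits the team to correct it.

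Several limits on the size of the effect do stand:
- Exact cancellation and exact thirds require the same standardised benefit on all six tasks.
- Full cancellation in EFcomp also requires higher delay aversion to be worse, which the SAP only implies. SWM and IED are the only EF components named as errors.
- One third describes the mean difference. Mixed signs also shrink the composite's SD when tasks correlate, so MEMcomp keeps 0.56 of the standardised effect at ρ = 0.3 and 0.68 at ρ = 0.5. The power figures already allow for this.
- Type I error is not inflated.
- Objective 2 is not lost for good, because the component scores can be recombined correctly.

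None of these makes the written formulas right. Even on the most favourable reading of delay aversion, an equal benefit leaves EFcomp with one third of the mean difference.

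**Conclusion.** The concern holds, and the formulas must be corrected before they are used. As written, two of the three primary outcomes contradict the SAP's own hypothesis. For an equal benefit d on each task, EFcomp has an expected difference of 0 (d/3 if delay aversion were scored higher-is-better) and MEMcomp has d/3, against d when oriented. With unequal benefits a true improvement can appear as harm. The signs of the four error scores follow from the SAP's own component definitions. The sign of delay aversion is inferred. The power figures rest on assumed values of d and ρ and on the age-7 sample size, and they show only the order of the loss.

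**What to change.** State for each component whether a higher score is better or worse, and confirm the direction of delay aversion from the task's scoring definition. Then orient every term before averaging:

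- EFcomp = (zSOC + zOTS − zSWM errors + zBDS − zCGT delay aversion − zIED errors)/6, where the CGT sign assumes that higher delay aversion is worse.
- MEMcomp = (−zVPA errors − zPAL errors + zDMS + zPRM + zSSP + zFDS)/6.

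Add one sentence saying that a higher composite means better function. Date the correction and record whether it was made before anyone saw results by group. If either composite has already been computed, report which orientation was used.

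The cost is two corrected formulas and a few lines of text. No new data and no extra analysis are needed.
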